8.3 Statistical Analyses

Biostatisticians at the DCC, with the assistance of scientific programmers, have adapted or developed a number of statistical programs for analyzing study data. Data are analyzed for both data monitoring purposes, as described above, and for the purpose of detecting beneficial or adverse treatment effects. The DCC uses standard statistical packages such as SAS, S-PLUS, R, and Stata to perform statistical analyses. The specific analysis plans follow:

8.3.1 Baseline Analyses

Although the stratified random assignment of participants to the various treatments should ensure comparability with respect to known and unknown variables, imbalance may occur by chance. Descriptive statistics for baseline characteristics, known or suspected to be associated with outcomes, will be prepared for the treatment groups. The variables considered in such a description can be categorized as: 1) demographic characteristics; 2) medical history; 3) physical examination; 4) laboratory data; and 5) quality of life and psychosocial data. Exact testing for categorical variables and Wilcoxon two sample rank sum test for continuous variables will be used to evaluate the differences in baseline variables between treatment groups.

8.3.2 Outcome Analyses

All analyses will be performed on two cohorts; (1) the randomized cohort, and (2) the total cohort (randomized plus the six patients who received open label therapy in a nonrandomized fashion).

8.3.2.1 Safety Evaluations

To demonstrate the relative safety of allo-MSCs when compared with placebo, the following analyses will be carried out, and the data tabulated and analyzed by therapy group (Fisher's Exact Test) between baseline and a) 6 months and b) 12 months:

1. Major adverse cardiac events (MACE) including death, hospitalization for worsening heart failure (HF), and/or exacerbation of HF (non-hospitalization)
2. Other significant clinical events including non-fatal stroke, non-fatal myocardial infarction, coronary artery revascularization, ventricular tachycardia/fibrillation, pericardial tamponade, infectious myocarditis, hypersensitivity reaction, neoplasm, or any other potential deleterious late effects detected and corroborated by clinical presentation, laboratory investigations, image analysis, and when necessary with biopsy from suspected target sites in the body
3. All adverse events (AEs) at least grade 2 in severity (see section 7.3.1)

8.3.2.2 Feasibility Evaluations

To assess the practicality of study procedures, the following measures will be reported. IRB-2013-0443 HSC-SPH-15-0443

CONFIDENTIAL AND PROPRIETARY

The number and percent of subjects who:

1. Have events between randomization and SPI that preclude the subjects from getting SPI
2. Receive less than 20 injections during the SPI procedure
3. Do not receive the intended dose of cells (100 million), reason, and actual dose delivered
4. Have at least one cardiac MRI endpoint measure that is uninterpretable due to issues related to the device, including, but not limited to, inability to undergo the procedure
5. Fail to complete follow-up

8.3.2.3 Prospectively Declared Efficacy Endpoints

To explore whether allo-MSCs produce a trend toward improved LV function and functional status when compared with placebo, the following domains¹¹¹ and measures will be evaluated:

- Myocardial evaluations by cMRI over time:
 - Function:
 - Change in LVEF
 - Change in global and regional strain (HARP MRI)
 - Structure:
 - Change in LVEDVI
 - Change in LVESVI
 - Change in LV Sphericity Index
 - Morphology:
 - Change in area of injury (e.g., inflammation, edema, fibrosis)
- Functional capacity over time:
 - Change in exercise tolerance (6MWT)
 - Change in MLHF Questionnaire (subject reported)
- Clinical outcomes over time:
 - MACE
 - Change in days alive and out of hospital
- Biomarkers over time:
 - Change in NT-proBNP

All endpoints listed above are continuous and will be assessed with the following approaches.

1. Examination of departures from normality will be assessed. A general linear mixed model approach: The within subject component of the twelve-month evaluation will reflect the measures obtained at baseline, six months, and twelve months. The between subject component will reflect the effects of the cell types (allo-MSCs versus placebo). We are interested in testing whether the trajectory over time of the change in each of the endpoints above is modified by treatment (allogeneic versus placebo.)
2. The Wilcoxon two sample rank sum test, comparing the changes in the endpoint variables from a) baseline six months and b) baseline to twelve months.

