20. Coagulopathy (INR > 1.5) not due to a reversible cause (e.g., warfarin and/or Factor Xa inhibitors) (see Section 6.4 re: injection procedure and anticoagulation therapy) *Note: Subjects who cannot be withdrawn from anticoagulation will be excluded.*
21. Presence of LV thrombus (*see guidance in Section 6.6.3*)
22. Presence of a pacemaker and/or ICD generator with any of the following limitations/conditions:
 - manufactured before the year 2000
 - leads implanted < 6 weeks prior to consent
 - non-transvenous epicardial or abandoned leads
 - subcutaneous ICDs
 - leadless pacemakers
 - any other condition that, in the judgment of device-trained staff, would deem an MRI contraindicated
23. Pacemaker-dependence with an ICD (*Note: pacemaker-dependent candidates without an ICD are not excluded*)
24. A cardiac resynchronization therapy (CRT) device implanted < 3 months prior to consent
25. Other MRI contraindications (e.g. patient body habitus incompatible with MRI)
26. An appropriate ICD firing or anti-tachycardia pacing (ATP) for ventricular fibrillation or ventricular tachycardia within 30 days of consent
27. Ventricular tachycardia ≥ 20 consecutive beats without an ICD within 3 months of consent, or symptomatic Mobitz II or higher degree atrioventricular block without a functioning pacemaker within 3 months of consent
28. A history of drug abuse (use of illegal "street" drugs except marijuana, or prescription medications not being used appropriately for a pre-existing medical condition) or alcohol abuse (≥ 5 drinks/day for > 3 months), or documented medical, occupational, or legal problems arising from the use of

alcohol or drugs within the past 24 months

29. Cognitive or language barriers that prohibit obtaining informed consent or any study elements (interpreter permitted)
30. Participation (currently or within the previous 30 days) in a cardiac related investigational therapeutic (including stem cell based therapies) or device trial
31. Pregnancy, lactation, plans to become pregnant in the next 12 months, or is unwilling to use acceptable forms of birth control during study participation
32. Any other condition that, in the judgment of the Investigator or Sponsor, would be a contraindication to enrollment, study product administration, or follow-up

Primary Endpoints

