Safety: To demonstrate the relative safety of allo-MSCs when compared with placebo, the following safety data will be collected and analyzed by therapy group between baseline and a) 6 months and b) 12 months:

1. Major adverse cardiac events (MACE) including: death, hospitalization for worsening heart failure (HF), and/or other exacerbation of HF (non-hospitalization)
2. Other significant clinical events including: non-fatal stroke, non-fatal myocardial infarction, coronary artery revascularization, ventricular tachycardia/fibrillation, pericardial tamponade, infectious myocarditis, hypersensitivity reaction, neoplasm, and/or any other potential deleterious late effects detected and corroborated by clinical presentation, laboratory investigations, image analysis, and when necessary with biopsy from suspected target sites in the body
3. All adverse events (AEs) at least grade 2 in severity

Feasibility: To assess the practicality of study procedures, the following measures will be reported.

The number and percent of subjects who:

1. Have events between randomization and SPI that preclude the subjects from getting SPI
2. Receive less than 20 injections during the SPI procedure
3. Do not receive the intended dose of cells (100 million), reason, and actual dose delivered
4. Have at least one cardiac MRI endpoint measure that is uninterpretable due to issues related to the device, including, but not limited to, inability to undergo the procedure
5. Fail to complete follow-up

Secondary Endpoints

Prospectively Declared Efficacy Endpoint Measures:

To explore whether allo-MSCs produce a trend toward improved LV function and functional status when compared with placebo, the following domains and measures will be evaluated:

- Myocardial evaluations by cMRI over time:
 - Function:
 - Change in LVEF
 - Change in global and regional strain (HARP MRI)
 - Structure:
 - Change in LVEDVI
 - Change in LVESVI
 - Change in LV Sphericity Index
 - Morphology:
 - Change in area of injury (e.g., inflammation, edema, fibrosis)
- Functional capacity over time:
 - Change in exercise tolerance (6MWT)
 - Change in MLHF Questionnaire (subject reported)
- Clinical outcomes over time:
 - MACE
 - Cumulative days alive and out of hospital
- Biomarkers over time:
 - Change in NT-proBNP

Duration of Study Follow-Up: Following discharge from the hospital, subjects will be assessed at week 1, and months 1, 6, and 12 (including assessment for cancer recurrence).

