3.3 Study Treatment Assignments and Dosages

Approximately thirty-six (36) subjects (including six actively treated lead-in participants and up to thirty-one randomized clinical trial participants) will be enrolled. The six subjects participating in the open-label lead-in will receive allo-MSC as described below in Group A. The remaining subjects will be randomized 1:1 to one of two treatment strategies:

- Group A – Receive allo-MSCs: 20 endomyocardial injections of 5 million cells each (for a total of 100 million allo-MSCs); with each injection administered in a volume of 0.4ml

IRB NUMBER: HSC-SPH-15-0443
UTHealth IRB APPROVAL DATE: 10/19/2018
The University of Texas
Health Science Center at Houston

CONFIDENTIAL AND PROPRIETARY

- Group B – Receive placebo: 20 endomyocardial injections of cell-free Buminate solution; with each injection administered in a volume of 0.4 ml.

The study product for Group A will be supplied from an allogeneic human MSC source (Appendix A); cells will be isolated from bone marrow of normal human donors and manufactured at a CCTRN cell manufacturing facility (CMF). Administering 20 injections of 0.4 ml each provides 8.0 ml of total study product volume with a cell concentration of 12.5 million total cells per ml, or 5 million cells per injection site. Twenty injections will be performed to treat the entire left ventricle (see section 5.4).

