8.4 Subgroup Evaluations

The effect of subgroup stratum on the relationship between cell delivery and the endpoints will be assessed. If a treatment effect is demonstrated, it is not likely to behave identically among all important subgroups. The subgroups of interest are age, gender, race, diabetes, hypertension, presence of a cardiac device, type of malignancy, baseline LVEF≤40% vs >40%, and number of cells delivered. For each endpoint, the effect of therapy will be determined within each subgroup stratum using the mixed general linear model with the subgroup strata as an explainer variable collection (i.e., a subgroup with p stratum will have $p-1$ indicator variables). SB Interactive 15-0443

CONFIDENTIAL AND PROPRIETARY

models are likely to be underpowered in this relatively small study. These additional analyses can sometimes be helpful in identifying extreme differences in the effects of treatment among subgroups, although the literature wisely warrants that caution be used in interpreting subgroup analyses.

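### Section 8.4 asks for a treatment effect by number of cells delivered although placebo contains none, and 8.3.2.3 analyses MACE as continuous although 8.3.2.1 uses Fisher's exact test

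*Combined protocol and SAP*

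**What the plan says.** **Cells delivered.** Section 8.4 states that for each endpoint "the effect of therapy will be determined within each subgroup stratum using the mixed general linear model", and its list of subgroups ends with "baseline LVEF≤40% vs >40%, and number of cells delivered". Section 3.3 defines Group B as "Receive placebo: 20 endomyocardial injections of cell-free Buminate solution". Section 8.3.2.2 already reports, as a feasibility measure, the subjects who "Do not receive the intended dose of cells (100 million), reason, and actual dose delivered".

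**MACE.** Section 8.3.2.3 lists MACE under clinical outcomes and says "All endpoints listed above are continuous and will be assessed with the following approaches". The approaches are a general linear mixed model on baseline, 6 and 12 months, testing whether treatment modifies the trajectory, and a Wilcoxon rank sum test on change to 6 and to 12 months. Section 8.3.2.1 has the same composite "analyzed by therapy group (Fisher's Exact Test) between baseline" and 6 months, and baseline and 12 months. In the Executive Summary, safety MACE stands under "Primary Endpoints" ("To demonstrate the relative safety of allo-MSCs when compared with placebo, the following safety data will be collected and analyzed by therapy group"); efficacy MACE is secondary. Section 8.6 reads p-values at a nominal 0.05 without adjustment.

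**Days alive and out of hospital.** Section 8.3.2.3 calls this a change; section 3.4.3 and the Executive Summary call it cumulative.

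**Baseline.** Section 8.3.2.3 uses baseline as one of the repeated responses. It does not say whether baseline means are constrained to be equal across arms.

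**The concern.** A treatment effect within a stratum needs subjects from both arms in that stratum. Every placebo subject has zero cells, so any stratum with cells contains only active subjects. Comparing each dose level with placebo can be fitted, but that groups subjects by something observed after randomisation. It is not a subgroup effect of therapy.

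MACE is a composite of events, not a continuous measure. If it is counted from Day 0, every subject's baseline value is 0, so the mixed model has a response with no variance at one of its three time points. Two sections also prescribe different tests for the same events at the same significance level. The listing of safety MACE as primary favours Fisher, but the plan still orders the rival tests. MACE could then be reported as significant in the efficacy section and not in the primary safety section. Days alive and out of hospital has the same all-zero baseline if counted from Day 0.

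**Working it through.** The plan gives no figure on these points to reproduce. Inputs from the documents are 15 subjects per arm (Executive Summary), six further open-label active subjects in the total cohort (8.3.2) and nominal 0.05 (8.6), taken as two-sided because sidedness is not stated. Event rates, event timing, covariance structure, correlations and partial-delivery counts are assumptions.

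**1. Cells delivered.** Take strata of 0, under 100 million and 100 million cells. The columns are the intercept, T (active), S1, S2, T×S1 and T×S2. With no placebo subject in S1 or S2, T×S1 = S1 and T×S2 = S2. If every active subject receives some cells, T = S1 + S2. Three of the six columns are redundant, so the rank is 3. Numerical checks agree with 3 and 12 active subjects in S1 and S2 (randomised cohort) and with 4 and 17 (total cohort). If all active subjects receive 100 million, the rank is 2. If one active subject is uninjected and kept under intention-to-treat, the rank is 4. The only contrast gained is in the zero-cell stratum, between placebo and active subjects never treated.

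**2a. Fisher against Wilcoxon, MACE coded 0/1, 15 v 15.**

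- Fisher for 0 v k events: p = 2 × C(15,k)/C(30,k). For k = 4: 2 × 1365/27405 = 0.0996.
- Asymptotic Wilcoxon without continuity correction: z² = (N−1)(ad−bc)²/(product of the four margins). For 0 v 4: 29 × 60²/(15 × 15 × 4 × 26) = 4.46, so z = 2.11 and p = 0.035.

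| Events | Fisher | Wilcoxon |
|---|---|---|
| 0 v 3 | 0.224 | 0.073 |
| 0 v 4 | 0.100 | 0.035 |
| 0 v 5 | 0.042 | 0.016 |

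Over all 16 × 16 = 256 tables, 20 conflict at 0.05, always with Wilcoxon significant and Fisher not (also 20 with a continuity correction). The conflict probability is therefore the difference in rejection rates. At equal rates of 10% it is 2.44 − 0.55 = 1.9%, and at 20% it is 4.33 − 1.67 = 2.7%; the values at 30% and 40% lie between. At 20 v 40%, 10 v 30%, 20 v 50% and 10 v 40% it is 8-14%.

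An exact permutation Wilcoxon equals Fisher in all 256 tables. In the total cohort (21 v 15), 4 of 352 tables still differ at 0.05; for 6/21 v 0/15, the permutation Wilcoxon gives 0.063 and Fisher 0.030.

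**2b. Mixed model.** Assume a random intercept, complete data and cumulative 0/1 responses. For 0 v 4 with two events by month 6, the arm differences at baseline, 6 and 12 months are 0, 2/15 and 4/15.

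- Interaction sum of squares: 7.5 × 2 × (2/15)² = 0.267 on 2 df.
- Within-subject error: 4 × (2/3) − 15 × 2 × (2/15)² = 2.133 on 28 × 2 = 56 df, mean square 0.0381.
- F = 0.1333/0.0381 = 3.5, p = 0.037, against 0.100 for Fisher.

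Enumerating all event splits with half of events by month 6, this test and Fisher disagree in 3.4-4.1% of trials at equal rates of 10-40%, and in 11-17% at the four differences above. The size of the interaction test is 3.9-5.8%. The 12-month contrast from the same model has size 8.5-9.7%, against 0.5-1.7% for Fisher.

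**2c. Days alive and out of hospital.** If counted from Day 0, change and cumulative count are the same number, so the rank sum test is unaffected. The mixed model still has an all-zero baseline.

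**3. Baseline as covariate.** If baseline means are unconstrained and data complete, the 6- and 12-month contrasts equal raw change-score differences. The variance ratio, covariate-adjusted to change score, is (1+ρ)/2 × (1 + 1/(N−4)). With N = 30 it is 0.779, 0.883, 0.935, 0.987 and 1.0125 at assumed ρ of 0.5, 0.7, 0.8, 0.9 and 0.95. The randomised change-score comparison keeps its size (0.049-0.050 in simulation).

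**The case against.** **Much of the MACE conflict reflects Fisher's conservatism.** This stands in part. Fisher's size is only 0.5-1.7%, and at 20 v 40% the power is about 19% for Wilcoxon and 11% for Fisher. Disagreements at true differences are therefore mostly real effects that Fisher misses; only the equal-rate figures bear on false positives. The plan still does not say which result governs.

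**The conflict depends on the version of the test.** An exact Wilcoxon removes it at 15 v 15, but the plan does not specify that version, and the mixed-model conflict remains. The 8.5-9.7% size belongs to a contrast that section 8.3.2.3 does not declare and depends on the assumed random intercept. The declared trajectory test is close to nominal.

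**The plan already contains the damage.** Section 8.6 treats findings as preliminary and section 8.4 urges caution on subgroups. A rank-deficient model would also show itself when fitted. This limits the consequences. The caution in 8.4 concerns power and interpretation, however, not an effect that cannot be estimated.

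**Baseline adjustment is a preference.** Agreed; it is optional and its omission is not an error.

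**Fisher on efficacy MACE repeats the safety analysis, and handling of losses is unstated.** The repetition is real but harmless: one set of events then has one test. The second point is fair, since section 3.5 allows for 15% loss over 12 months.

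**Conclusion.** Both main points hold. The cells-delivered subgroup effect is not estimable in any stratum with cells, at any sample size and whatever the dose distribution. This follows from the design and needs no assumption. Declaring MACE continuous is wrong and gives it tests that compete with section 8.3.2.1. How often they conflict rests on 0/1 coding, assumed event rates and, for the mixed model, an assumed random intercept and event timing. With one third or two thirds of events by month 6 instead of half, the mixed-model conflict is 3.9-4.6% at equal rates and 12-19% at the same differences. The days-alive wording needs reconciling. These points should be corrected, but their effect on the trial's conclusions is limited.

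**What to change.** 1. **Section 8.4:** remove the number of cells delivered from the treatment-effect subgroups. Describe dose against outcome within the active arm only, labelled as non-randomised, using the doses already reported under 8.3.2.2.
2. **Sections 8.3.2.3 and 8.4:** take MACE out of the statement that all endpoints are continuous and out of the subgroup linear models. Use the exact test of 8.3.2.1, with a risk difference and 95% confidence interval at 6 and 12 months.
3. **Days alive and out of hospital:** use one definition throughout. Compare the cumulative count by rank sum at 6 and 12 months, without the mixed model. State here and for MACE how subjects lost before the time point are counted.
4. **Optional:** for the endpoints that are continuous, use baseline as a covariate, with Wilcoxon on change as a sensitivity analysis. The alternative is a common baseline mean, in the randomised cohort only because the total cohort adds six non-randomised subjects; this already captures most of the gain. No gain is claimed for centre adjustment, since the documents do not give what is needed to judge it.

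The cost is wording and a few lines of code, with no new data and no change in sample size. The optional covariate uses 1 degree of freedom and loses about 1% of precision if the correlation is near 0.95.

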3.5 Sample Size

This phase I study will recruit approximately 36 subjects who will have baseline and follow-up assessments to assess the changes over time in LV function and functional status. It is hoped that we will establish the precision of these estimates ¹¹¹. These measures will then be used to adequately power subsequent studies that will be able to determine the effect of therapy with statistical regularity and precision. The following measures will be assessed:

1. LV End Diastolic Volume (LVEDV) Index
2. LV End Systolic Volume (LVESV) Index
3. LV Ejection Fraction (LVEF)
4. Area of Injury (e.g., inflammation, edema, fibrosis)
5. Sphericity Index criteria
6. MLHF Questionnaire
7. Exercise tolerance (6MWT)
8. Global and regional strain

This study will recruit 31 patients with the addition of 6 patients to account for loss-to-follow-up. Subjects will be followed for one year; this is six months more than our FOCUS study which experienced a 10% follow-up loss rate. Increasing the estimation for loss-to-follow-up in SENECA to 15% over the 12 month course of follow-up would produce 4.5 patients potentially lost, administratively rounded up to 6 patients.

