8.0 STATISTICAL PROCEDURES

8.1 Randomization Strategy and Monitoring

Randomization, or the random allocation of therapy, is a well-accepted mechanism for reducing potential bias in evaluating treatment effects. Randomization process, timing, and notification details are provided in section 4.6 above. Subjects will be randomized either to allo-MSCs or to placebo stratifying by center and using block sizes of 2.

The DCC will monitor recruitment by providing reports to the NHLBI Project Office as appropriate during the recruitment phase. Updated reports will be maintained on an Internet site accessible to Network members. Goals for recruitment will be set and will be reviewed by the DCC and the NHLBI Project Office.

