8.6 Multiplicity Issues

This is the first study evaluating the effect of mesenchymal cells in patients with anthracycline-induced cardiomyopathy. No adjustments will be made for multiple comparisons. The reported measures of effect will be effect size, the standard error of the effect size, the 95% confidence interval for the effect size and the p-value. P-values will be interpreted at nominal 0.05 levels. Because of the high false discovery rate in our study, the findings from our study cannot be accepted by the research community as confirmatory, but must be treated as preliminary, requiring an additional study to confirm the SENECA results.

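### Neither efficacy method as written adjusts for the baseline value or for centre, so treatment effects are valid but less precise than they could be at no real cost

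*Combined protocol and SAP*

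**What the plan says.** Section 8.3.2.3 specifies the efficacy analysis in two parts.

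- **Mixed model.** "The within subject component of the twelve-month evaluation will reflect the measures obtained at baseline, six months, and twelve months". On the other side, "The between subject component will reflect the effects of the cell types (allo-MSCs versus placebo"). The test is whether treatment modifies the trajectory over time.
- **Rank test.** "The Wilcoxon two sample rank sum test, comparing the changes in the endpoint variables", from baseline to 6 months and from baseline to 12 months.

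Section 8.1 randomises "stratifying by center and using block sizes of 2"; centre does not reappear in the analysis sections. Section 8.3.1 tests baseline differences between arms but attaches no consequence to them. Section 8.4 uses baseline LVEF (at or below 40% versus above) only to define a subgroup.

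Section 8.6 sets out what will be reported: "The reported measures of effect will be effect size, the standard error of the effect size, the 95% confidence interval for the effect size", with a p-value. Section 3.5 gives the purpose of the measurements: "It is hoped that we will establish the precision of these estimates", so that later studies can be powered. Under section 8.3.2 every analysis is run on two cohorts: "1) the randomized cohort, and (2) the total cohort", the second adding the six open-label subjects.

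**The concern.** Having baseline in the response vector is not the same as adjusting for it. If each arm has its own baseline mean, which is the natural meaning of a treatment term plus a treatment-by-time interaction, the estimated effect at a visit is the difference in mean change. The rank test also uses raw change. Raw change fixes the coefficient on baseline at 1, whereas adjustment estimates it. When the baseline/follow-up correlation is moderate, the fixed coefficient adds avoidable variance.

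At stake are the SEs and 95% CIs that section 8.6 promises, from about 15 subjects per arm, and their use in planning later trials. As specified, the rank test yields only a p-value, so those figures would have to come from the mixed model. The text does not state the baseline parameterisation, so two analysts could follow the same plan and report different SEs. Efficacy is a secondary, exploratory aim; the primary safety and feasibility analyses are not affected.

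**Working it through.** **Inputs.** About 30 randomised 1:1 (sections 3.2 and 3.3), so n = 15 per arm and N = 30. A loss to follow-up of 15% over 12 months (section 3.5). A 95% CI (section 8.6). The baseline/follow-up correlation ρ is not given; 0.5, 0.7, 0.8 and 0.9 are assumed, with equal SDs set to 1. The number of centres is not given either.

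**The plan's own figure.** Section 3.5 contains the only sample-size arithmetic: 0.15 × 30 = 4.5, which the plan rounds up to 6. The same rate applied to one arm gives 15 × 0.85 = 12.75, taken as 13 per arm.

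**Step 1: what the mixed model estimates.** With separate arm means, a compound-symmetric covariance and complete data at three visits, the variance of the month-12 effect is 4(1−ρ)/15 = 0.1333, 0.0800, 0.0533 and 0.0267. This is identical to the variance of the difference in raw change. Mixed models fitted to simulated complete data sets gave interaction estimates equal to the differences in mean change, to rounding.

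**Step 2: gain from adjusting for baseline.**

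- Raw change: Var = 2(1−ρ) × 2/n
- Adjusted: Var = (1−ρ²) × 2/n × [1 + 1/(N−4)]
- Ratio: (1+ρ)/2 × [1 + 1/(N−4)]

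At ρ = 0.5, raw change gives 4 × 0.5/15 = 0.1333 (SE 0.365). Adjusted gives 0.75 × 2/15 × 27/26 = 0.1038 (SE 0.322). The ratio is 0.779. A simulation of 40,000 trials per setting, with t-based intervals, agrees:

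| ρ | SE raw | SE adjusted | Variance ratio, formula | Variance ratio, simulated | CI width ratio, 15 per arm | CI width ratio, 13 per arm |
|---|---|---|---|---|---|---|
| 0.5 | 0.365 | 0.322 | 0.779 | 0.774 | 0.884 | 0.888 |
| 0.7 | 0.283 | 0.266 | 0.883 | 0.884 | 0.940 | 0.944 |
| 0.8 | 0.231 | 0.223 | 0.935 | 0.934 | 0.967 | 0.971 |
| 0.9 | 0.163 | 0.162 | 0.987 | 0.986 | 0.994 | 0.999 |

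Mean CI width at 15 per arm goes from 1.48 to 1.31, 1.15 to 1.08, 0.94 to 0.91, and 0.66 to 0.66 SD. Type I error for raw change was 0.049 to 0.050. Setting the ratio to 1 gives the break-even correlation: ρ = 2 × 26/27 − 1 = 0.93.

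**Step 3: incomplete data.** With 2 of 15 per arm missing month 12, the variance of the common-baseline model relative to the separate-means model is 0.773, 0.865, 0.910 and 0.955, before any cost of estimating the covariance. The gain does not depend on complete data.

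**Step 4: LVEF.** Entry requires LVEF of 45% or less (section 4.3), which can truncate the baseline spread. As an illustration only, suppose entry keeps the lower half of a normal distribution, with slopes of 0.5, 0.7, 0.8 and 0.9. The CI width ratios are then 0.963, 0.989, 1.000 and 1.010.

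**Step 5: centre.** If centre explains nothing, fixed centre terms for 4 to 8 assumed centres widen the CI by about 0.5% to 1.3%. In a separate simulation with blocks of 2, 5 or 7 centres and an assumed intraclass correlation of 0.1 to 0.2, leaving centre out gave a reported SE of about 0.36 against 0.32 to 0.34 with centre, and type I error of 0.033 to 0.044. The unadjusted estimator's true SE was about 0.33 to 0.35, so the fault there is mainly an overstated SE. At zero correlation there was no gain.

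**The case against.** **The mixed model might already adjust.** A version with a common baseline mean fits the same words and would match covariate adjustment. The text does leave this open. But nothing states the constraint, and a between-subject treatment effect with a trajectory interaction ordinarily means separate means. If the constraint was intended, one sentence settles it.

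**The gain is small and is an average.** This stands. At ρ = 0.9 it is negligible. In a single trial at 15 per arm, the adjusted CI would be wider than the raw-change CI about 9%, 23%, 36% and 56% of the time for the four correlations; under the LVEF truncation illustration, 35%, 51%, 60% and 70%. Stable therapy before entry, core-laboratory reading and repeated walk tests could push correlations upward. That limits the importance of the point but does not favour leaving the analysis unspecified.

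**Centre adds no demonstrated precision.** Also true. The reason to include it is to analyse as randomised, and any further benefit needs between-centre variation, which the documents do not describe.

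**Planning quantities can be computed later from the same data.** Correlations and adjusted SDs can be. The SE and CI promised in section 8.6 would still be the wider ones, or the choice of model would be made after the data were seen.

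**Stakes are low.** Section 8.6 itself calls the findings preliminary. This is a reason to rank the change as advisable rather than essential.

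**Conclusion.** The concern holds. As written, neither method names an adjustment for baseline or centre, and on the natural reading both estimate or test raw change. In the randomised cohort this is valid. The average cost is a 95% CI wider than it need be: adjustment would narrow it by about 12%, 6%, 3% or 0.6% at 15 per arm, and 11%, 6%, 3% or 0.1% at 13 per arm, for assumed correlations of 0.5, 0.7, 0.8 or 0.9. For LVEF the illustrated range runs from 4% narrower to 1% wider. These figures rest on equal SDs and on correlations that the documents do not supply. Centre is a matter of matching the analysis to the randomisation, with no precision gain claimed. The change is worth making because it is cheap and serves the plan's own aim of precision; the trial's validity does not depend on it.

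**What to change.** Amend section 8.3.2.3 for measures that have a baseline value; this excludes MACE and days alive and out of hospital.

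1. In the randomised cohort, fit the mixed model to the 6- and 12-month values with treatment, visit, treatment-by-visit, baseline and baseline-by-visit. Alternatively, keep baseline as a response and state that the arms share a common baseline mean.
2. Take the effect size, SE and 95% CI of section 8.6 from that model.
3. Include centre, for example as a random effect with small centres pooled.
4. Do not carry the common-mean constraint into the total cohort. It rests on randomisation, and the six open-label subjects were not randomised.
5. Keep the Wilcoxon test on change as a sensitivity check.

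The cost is SAP wording, about one degree of freedom per visit for baseline, and a slight possible widening from centre or where the correlation is about 0.93 or above. No new data are needed.
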